## 9.4. Key Elements of Analysis Plan

### 9.4.1. Primary Analyses

The primary endpoint in this study is the change from baseline in the daily average number of urinary incontinence episodes at week 6 after the first treatment.

This will be analyzed using a mixed model for repeated measures (MMRM). This model will include the treatment group, visit, patient etiology and treatment-by-visit interaction as fixed factors and baseline values as a covariate. An unstructured variance structure will be used to model the within-subject errors, shared across treatments. Analysis will be done with the MIXED procedure in SAS, using the Kenward-Roger option to estimate denominator degrees of freedom and standard errors. Least-squares mean and its two-sided 95% confidence intervals will be estimated. The dataset including only data until week 12 after the first treatment will be used for MMRM.

If the number of subjects for a given etiology group is too few to analyze, then the patient etiology will be excluded from the model.

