No formal statistical tests will be done, therefore no adjustment for multiplicity will be made for secondary endpoints.

If the number of subjects for a given etiology group is too few to analyze, then the patient etiology will be excluded from the models.

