5.4. Examination of Covariates, Other Strata and Subgroups

5.4.1. Covariates and Other Strata

The list of covariates and other strata may be used in descriptive summaries and statistical analyses, some of which may also be used for subgroup analyses. Additional covariates and other strata of clinical interest may also be considered.

Category	Item	Details
Strata	NDO etiology (SCI with neurological injury level C5 to C8, SCI with neurological injury level T1 or below, or MS)	This is the randomization strata factor. This factor will NOT be included in all statistical model, because the numbers of subjects of SCI with neurological injury level C5 to C8 and MS are small. Descriptive summaries results will also not be provided by each category.
Covariate	Nothing	Considering small number of subjects in this study, subgroup analysis will not be meaningful.

•

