6.1.3. Demographic and Baseline Characteristics

Each of the following types of data will be summarized in each treatment group and total:

- Demographic data (age, sex, ethnicity, weight, height, body mass index (BMI), race and racial combinations)

- Baseline disease characteristics
 - Items of diary data
 - ✧ Daily average episodes of urinary incontinence
 - ✧ Daily average episodes of voids
 - ✧ Average volume voided per void
 - PVR volume and number and percentage of subjects with its category (no measurement of PVR, < 100 mL, >= 100 mL to < 200 mL, >= 200 mL to < 350 mL or >= 350mL)
 - Duration of NDO history
 - Number and percentage of subjects with NDO etiology (SCI with neurological injury level C5 to C8, SCI with neurological injury level T1 or below, or MS)
 - (For subject with SCI only): Number and percentage of subjects with ASIA (American Spinal Injury Association) impairment scale (A: complete, B: sensory incomplete, C: motor incomplete, D: motor incompletes or E: normal)
 - Number and percentage of subjects of void pattern (CIC only, Mixed (catheterization and spontaneous void), Spontaneous void only, Mixed (Intermittent balloon catheter and spontaneous void), CIC and Intermittent balloon catheter or Mixed (CIC, Intermittent balloon catheter and spontaneous void))
 - Urodynamics
 - ✧ Maximum cystometric capacity (MCC)
 - ✧ Maximum detrusor pressure during the first involuntary detrusor contraction (IDC) ($P_{\max IDC}$)
 - ✧ Volume at first involuntary detrusor contraction ($V_{P_{\max IDC}}$)
 - ✧ Maximum detrusor pressure during the storage phase ($P_{\det Max}$)
- Age ranges (for EudraCT requirement)

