7.1.4. Strategy for Intercurrent (Post-Randomization) Events

Following strategy will be planned for intercurrent events. Note that these strategies will be applied for the data until 12 weeks after first administration.

Intercurrent Events	Strategy
Treatment discontinuation / Study withdrawal	Considering the characteristics of study treatment, treatment discontinuation is not defined in this study. In primary analysis, the missing data after study withdrawal will not be imputed and treated as missing. This means it is assumed that missing mechanism is missing-at-random for primary endpoint. This study is not designed to confirm formal statistical hypothesis, so sensitivity analysis will not be done.
Use of protocol inhibited medication	Not planned any specific handling for use of protocol inhibited medication.
Use of rescue medication	Rescue medication is not defined in this study.

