7.1.5.1. Statistical Methodology Specification

Endpoint / Variables

 • Change from baseline in the daily average number of urinary incontinence episodes at week 6 after the first treatment 
 ○ “Daily average” means “Daily frequency calculated by 3-day dairy”. More detail for calculation methods will be in section 11.6.3
Model Specification

 • The endpoint will be analyzed using a mixed model for repeated measures (MMRM). • Terms fitted in the MMRM model will include: 
 • Fixed, categorical effects: treatment, visit, treatment-by-visit interaction • Fixed, continuous effects: baseline daily average number of urinary incontinence episodes, baseline-by-visit interaction • Since the numbers of subjects of both SCI with neurological injury level C5 to C8 and MS are small, NDO etiology will not be included in MMRM, as described in study protocol. • An unstructured variance structure will be used to model the within-subject errors, shared across treatments. • The Kenward-Roger option in SAS PROC MIXED will be used to estimate denominator degrees of freedom and standard errors.
Model Checking & Diagnostics

 • The Kenward and Roger method for approximating the denominator degrees of freedom and correcting for bias in the estimated variance-covariance of the fixed effects will be used. • An unstructured covariance structure for the R matrix will be used by specifying ‘type=UN’ on the REPEATED line. 
 ○ In the event that this model fails to converge, alternative correlation structures may be considered such as CSH or CS. • Akaike's Information Criteria (AIC) will be used to assist with the selection of covariance structure.
Model Results Presentation

 • Adjusted means (least square means: LS means) and corresponding standard errors (SEs) of means will be presented for each treatment by visit, together with estimated treatment differences (GSK1358820 – Placebo), the corresponding 95% confidence intervals. The primary treatment comparison will be the contrast between treatments at week 6 after the first treatment. • Plots of LS means and SEs from the model will be generated for each treatment by visit.
Data included in Model

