
 The endpoints will be analyzed using an analysis of covariance (ANCOVA) model. Terms fitted in the ANCOVA model will include: 
 Fixed, categorical effects: treatment Fixed, continuous effects: baseline value Since the numbers of subjects of both SCI with neurological injury level C5 to C8 and MS are small, NDO etiology will not be included in MMRM, as described in study protocol. The Kenward-Roger option in SAS PROC MIXED will be used to estimate denominator degrees of freedom and standard errors.
Model Results Presentation

 Adjusted means (LS means) and corresponding SEs of means will be presented for each treatment by visit, together with estimated treatment differences (GSK1358820 – Placebo), the corresponding 95% confidence intervals.

Secondary Statistical Analyses for change from baseline after first treatment
Endpoint(s)

 Change from baseline at week 6 after the first treatment 
 Maximum cystometric capacity (MCC) Maximum detrusor pressure during the first involuntary detrusor contraction (IDC) ($P_{\max IDC}$) Volume at the first involuntary detrusor contraction ($V_{P_{\max IDC}}$) Maximum detrusor pressure during the storage phase ($P_{\det Max}$) KHQ domain score (role limitations, social limitations)
Model Specification

 Same as “Secondary Statistical Analyses for change from baseline after week12 after first treatment”.
Model Results Presentation

 Same as “Secondary Statistical Analyses for change from baseline after week12 after first treatment”.

Secondary Statistical Analyses for Binary data
Endpoint(s)

 Proportion of subjects attaining 100%, $\geq 75\%$ and $\geq 50\%$ reduction from baseline in the daily average of urinary incontinence episodes Proportion of subjects with positive response on the TBS
Results Presentation

 The number and percent of subjects who met each endpoint will be summarized by treatment and visit. The odds ratio and its 95% confidence interval will also be presented.
Missing Data

 Missing data until week 12 after first treatment will be treated as non-responder or no positive response. Missing data after week 12 after first treatment will be treated as missing.

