11.10.5. Study Population Tables

Study Population Tables						
No.	Population	IDSL / TST ID / Example Shell	Title	Programming Notes	Report at Interim	Report at Final
Subject Disposition						
1.1.	FAS1	ES1	Summary of Subject Disposition	ICH E3, GSK CTR, FDA, FDAAA, EudraCT	Y	Y
1.2.	Screened	ES4	Summary of Participant Disposition at Each Study Epoch	ICH E3	Y	Y
1.3.	Screened	ES6	Summary of Screening Status and Reasons for Screen Failure	Journal Requirements	Y	
1.4.	FAS1	NS1	Summary of Number of Subjects by Site ID	EudraCT		Y
Protocol Deviation						
1.5.	FAS1	DV1	Summary of Important Protocol Deviations	ICH E3	Y	Y
Population Analysed						
1.6.	Screened	SP1	Summary of Study Populations	IDSL	Y	Y
Demographic and Baseline Characteristics						
1.7.	FAS1	DM1	Summary of Demographic Characteristics	ICH E3, GSK CTR, FDA, FDAAA, EudraCT	Y	
1.8.	FAS1	DM1	Summary of Baseline Disease Characteristics		Y	
1.9.	FAS1	DM5	Summary of Race and Racial Combinations	ICH E3, FDA, GSK CTR, FDA, FDAAA, EudraCT	Y	
1.10.	Enrolled	DM11	Summary of Age Ranges	FDA, FDAAA, EudraCT	Y	
Prior and Concomitant Medications						
1.11.	FAS1	CM1	Summary of Concomitant Medications	ICH E3	Y	Y

CONFIDENTIAL

204948

Study Population Tables						
No.	Population	IDSL / TST ID / Example Shell	Title	Programming Notes	Report at Interim	Report at Final
1.12.	FAS1	CM1	Summary of Prior or Concomitant NDO Medications		Y	
1.13.	FAS1	Non-Standard	Summary of Number of Subjects with Prior NDO Medication		Y	
1.14.	FAS1	Non-Standard	Summary of Number of Subjects with Concomitant NDO Medication at Baseline		Y	
1.15.	FAS1	Non-Standard	Summary of Primary Reason the prior NDO Medication NOT Considered to Adequately Manage the Symptom		Y	
Exposure and Treatment Compliance						
1.16.	SP1	Non-Standard POP_T1	Summary of Cumulative Duration of Follow-up in Overall	ICH E3	Y	Y
1.17.	SPDB	Non-Standard POP_T1	Summary of Duration of Follow-up in Double Blind Phase	ICH E3	Y	Y
1.18.	SP1	Non-Standard POP_T1	Summary of Duration of Follow-up in GTC1, GTC2 and GTC3	ICH E3		Y
1.19.	SPDB	Non-Standard POP_T2	Summary of Number of Study Treatment Injection		Y	Y

CONFIDENTIAL

204948

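### Is it a defect that the SAP leaves NDO etiology, the randomisation stratum, out of every model and plans no etiology-adjusted supportive analysis?

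*SAP*

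**What the plan says.** Protocol 4.4 and 6.2 stratify randomisation by NDO etiology: SCI at C5 to C8, SCI at T1 or below, or MS. Protocol 9.4.1 puts etiology in the primary MMRM, and 9.4.2 puts it in the secondary MMRM and ANCOVA models. Both sections add a condition. In 9.4.1 it begins "If the number of subjects for a given etiology group is too few to analyze", and etiology is then left out. The same condition in 9.4.2 ends "then the patient etiology will be excluded from the models". Neither gives a number.

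SAP 5.4.1 applies the condition to all models: "This factor will NOT be included in all statistical model, because the numbers of subjects of SCI" at C5 to C8 and of MS are small. SAP 7.1.5.1 repeats it for the primary model: "NDO etiology will not be included in MMRM, as described in study protocol". SAP 7.2.5.1 gives the same reason for the secondary models: "Since the numbers of subjects of both SCI with neurological injury level C5 to C8 and MS are small". The ANCOVA terms listed there are treatment and baseline only.

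The distribution of the strata is still reported. SAP 6.1.3 lists "Number and percentage of subjects with NDO etiology" by treatment group and in total, and SAP 11.10.5 places this in Table 1.8, "Summary of Baseline Disease Characteristics".

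**The concern.** A factor used to stratify randomisation normally goes into the analysis model. If it is prognostic and omitted, the standard error ignores the balance that stratification bought, and the confidence interval is wider than it need be. Three features sharpen the worry:

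- The exception has no threshold, so it could look like a free choice.
- The SAP goes straight from three levels to none, without trying SCI versus MS.
- The primary endpoint has a single MMRM table (Table 2.4), and no adjusted version stands beside it.

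SAP 7.1.4 also states "so sensitivity analysis will not be done", which can be read as closing off any supportive model. That sentence sits in the row on study withdrawal and concerns missing data, so it does not bear on etiology.

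At stake is the width of the Week 6 interval. With 30 subjects and no formal hypothesis (Protocol 9.1), the estimate and its interval are what readers will use.

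**Working it through.** **1. The plan's own figures.** Protocol 9.2.1 gives 15 per group, difference -1.5, SD 3.0, power 26%, and about 92% probability that the estimate favours active treatment.

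- SE = 3.0 × √(2/15) = 1.095, and 1.5/1.095 = 1.369.
- Two-sided 5% t-test power on 28 df = 26.2%.
- Φ(1.369) = 91.5%. With the quoted SDs 3.10 and 2.56, pooled 2.84, it is 92.6%.

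Both figures reproduce, and neither relies on etiology.

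**2. Is the exclusion a departure?** No. The protocol says to drop etiology if a group is too small. The SAP says two of the three groups are small and drops it. The undefined threshold would matter if the decision were still open at unblinding, but the SAP has closed it.

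**3. What omission costs.** The documents give neither stratum sizes nor etiology effects, so I assumed them. Simulation: ANCOVA at one visit, N = 30, 1:1 in blocks of 4 within stratum (assumed), residual SD 3.0, 6,000 trials per row, no true treatment difference. Sizes are C5-C8 / T1 or below / MS. Shift d means C5-C8 at +d and MS at -d relative to T1 or below. Percentages are relative to the width with etiology omitted.

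| Sizes | d | 95% CI width, omitted | Three levels | SCI vs MS | Rejection, omitted | Coverage, omitted |
|---|---|---|---|---|---|---|
| 2/26/2 | 0 | 4.54 | 4.66 (+2.6%) | 4.60 (+1.3%) | 4.8% | 95.2% |
| 4/22/4 | 0 | 4.54 | 4.56 (+0.4%) | 4.55 (+0.2%) | 4.5% | 95.5% |
| 6/20/4 | 0 | 4.52 | 4.56 (+0.9%) | 4.53 (+0.2%) | 4.7% | 95.3% |
| 2/26/2 | 1.5 | 4.63 | 4.67 (+0.9%) | 4.65 (+0.4%) | 5.1% | 94.9% |
| 4/22/4 | 1.5 | 4.71 | 4.57 (-3.0%) | 4.63 (-1.7%) | 4.1% | 95.9% |
| 6/20/4 | 1.5 | 4.73 | 4.57 (-3.4%) | 4.64 (-1.9%) | 4.5% | 95.5% |
| 2/26/2 | 3 | 4.85 | 4.67 (-3.7%) | 4.76 (-1.9%) | 4.2% | 95.8% |
| 4/22/4 | 3 | 5.15 | 4.57 (-11.3%) | 4.83 (-6.2%) | 2.8% | 97.2% |
| 6/20/4 | 3 | 5.30 | 4.60 (-13.2%) | 4.94 (-6.8%) | 2.8% | 97.2% |

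At d = 1.5 the width changes by between 4.57 - 4.73 = -0.16 and 4.67 - 4.63 = +0.04, that is -0.08 to +0.02 on each side.

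The point estimate hardly changes in accuracy. Its root mean squared error at 4/22/4 is 1.104 omitted against 1.106 with three levels at d = 1.5, and 1.125 against 1.122 at d = 3. Stratified allocation has already balanced the arms, so omission mainly makes the reported interval conservative.

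**4. Check by formula.** If the small strata hold a fraction p of subjects, omission raises the residual variance from σ² to about σ² + d²p. The width ratio is √(σ²/(σ² + d²p)), times the cost of adjustment from the d = 0 row.

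- 4/22/4, d = 1.5: d²p = 2.25 × 8/30 = 0.60; √(9/9.6) = 0.968; × 1.004 = 0.973, or -2.7% (simulated -3.0%).
- 2/26/2, d = 1.5: d²p = 2.25 × 4/30 = 0.30; √(9/9.3) = 0.984; × 1.026 = 1.010, or +1.0% (simulated +0.9%).

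**5. The MMRM itself.** A separate simulation used the MMRM with Kenward-Roger, 800 trials per setting, and assumed baseline correlation 0.5, so residual variance 9 × 0.75 = 6.75. It expresses etiology as R², the share of that variance it explains. The implied shift is d = √(R² × 6.75 × 30/m), with m subjects in the two small strata together.

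| Sizes | d at R² = 5% | Three levels | SCI vs MS | SCI vs MS interval wider in |
|---|---|---|---|---|
| 4/22/4 | 1.13 | -2.3% | -1.3% | 50% of trials |
| 3/24/3 | 1.30 | -1.8% | -1.1% | 55% |
| 2/26/2 | 1.59 | -0.4% | -0.2% | 62% |
| 1/28/1 | 2.25 | +0.6% | +0.4% | 67% |

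On a half-width of about 2.0, the largest of these changes is 0.023 × 2.0 = 0.05 episodes/day per side.

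**The case for a change.** The best opposing case is that pre-specification is cheap insurance. Nobody knows beforehand whether etiology is prognostic. A main effect costs at most 2 df (t critical value 2.052 on 27 df, 2.056 on 26), no simulated MMRM failed to fit even with one subject per small stratum, and the average loss when etiology is irrelevant is smaller than the gain when it matters strongly. SCI versus MS was also the sponsor's own stratification before Amendment 04. An adjusted estimate requested after the unblinded interim analysis would be post hoc.

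Much of this is true: the adjusted model is estimable, and analysing as stratified is a sound convention. It does not make the plan wrong, for three reasons.

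- The gain depends on effects for which the documents offer no evidence. At R² = 10% the implied shifts are 1.6, 1.8, 2.3 and 3.2 episodes/day for 4, 3, 2 and 1 subjects per small stratum. Each exceeds the assumed drug effect of 1.5, in opposite directions, after baseline adjustment.
- SCI versus MS keeps the small MS level that is part of the SAP's stated reason, and it gains nothing if the difference lies in C5-C8. At 2/26/2, MS fell wholly in one arm in about a third of simulated trials.
- Any cut-off chosen for an adjusted model, such as three subjects per stratum, would have no more basis in the documents than the present wording.

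What stands is that stating the stratum totals in the SAP would have let a reader check the exception sooner. Table 1.8 supplies them by arm.

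**Conclusion.** The concern does not hold. The exclusion follows the protocol's own rule, is explained and fixed in the SAP, introduces no bias, and leaves coverage at or slightly above nominal within simulation error. For shifts as large as the assumed drug effect, adding etiology changes each side of the Week 6 interval by -0.08 to +0.02 episodes/day at the sizes in the first table. With one subject per small stratum it widens the interval, by 1.3% to 2.7% in a further ANCOVA simulation. Only shifts near 3 episodes/day with four or more subjects per small stratum give a clear gain, up to 13%, and the unadjusted interval is then conservative, not invalid.

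This rests on assumed stratum sizes, block size, effect pattern and baseline correlation. It covers the statistical models only. A supportive adjusted model would be a reasonable preference, but in a feasibility-sized trial with 26% power and no formal hypothesis its absence changes no conclusion.

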5.4.2. Examination of Subgroups

Examination of subgroup will not be done in this study. Considering small subjects in this study, subgroup analysis will not be meaningful.

5.5. Multiple Comparisons and Multiplicity

This study is not designed to evaluate formal statistical hypotheses. Therefore, the multiplicity will not be adjusted for any endpoints.

5.6. Other Considerations for Data Analyses and Data Handling Conventions

Other considerations for data analyses and data handling conventions are outlined in the appendices:

Section	Component
11.3	Appendix 3: Assessment Windows

Section	Component
11.4	Appendix 4 : Study Phases and Treatment Emergent Adverse Events
11.5	Appendix 5 : Data Display Standards & Handling Conventions
11.5	Appendix 6 : Derived and Transformed Data
11.7	Appendix 7 : Reporting Standards for Missing Data

6. STUDY POPULATION ANALYSES

6.1. Overview of Planned Study Population Analyses

The study population analyses will be based on the “FAS1” population, unless otherwise specified.

Study population analyses including analyses of subject’s disposition, protocol deviations, demographic and baseline characteristics, prior and concomitant medications, and exposure and treatment compliance will be based on GSK Core Data Standards. Details of the planned displays are presented in [Appendix 10: List of Data Displays](#).

6.1.1. Subject Disposition and Populations

For FAS1 population, the number and percentage of subjects who completed the study as well as withdraw early from study will be summarized in each treatment group, along with the reasons for early withdrawal. In addition, the number and percentage of subjects of screening status (enrolled or failed) and the reason for screen failure will be summarized.

Using Screened population, the number and percentage of subjects in each treatment group and non-randomized subjects will be summarized by status (entered, completed or withdrawn) at each epoch (screening phase, double blind phase and open label phase).

The number and percentage of subjects at each centre and country will be summarized (this study includes only Japan as country, but country will be displayed) in each treatment group and total.

Using Screened population, the number of subjects in each population (Screened, passed screening phase (Enrolled), entered each phase (FAS1, FAS2, FAS3, SPDB, SP1, SP2, SP3)) will be summarized total and by treatment group (not including the screened population).

The subjects excluded from any FAS population or SP population will be only listed, not summarized.

6.1.2. Protocol Deviation

The number and percentage of subjects with important protocol deviation will be summarized.

6.1.3. Demographic and Baseline Characteristics

Each of the following types of data will be summarized in each treatment group and total:

- Demographic data (age, sex, ethnicity, weight, height, body mass index (BMI), race and racial combinations)

- Baseline disease characteristics
 - Items of diary data
 - ✧ Daily average episodes of urinary incontinence
 - ✧ Daily average episodes of voids
 - ✧ Average volume voided per void
 - PVR volume and number and percentage of subjects with its category (no measurement of PVR, < 100 mL, >= 100 mL to < 200 mL, >= 200 mL to < 350 mL or >= 350mL)
 - Duration of NDO history
 - Number and percentage of subjects with NDO etiology (SCI with neurological injury level C5 to C8, SCI with neurological injury level T1 or below, or MS)
 - (For subject with SCI only): Number and percentage of subjects with ASIA (American Spinal Injury Association) impairment scale (A: complete, B: sensory incomplete, C: motor incomplete, D: motor incompletes or E: normal)
 - Number and percentage of subjects of void pattern (CIC only, Mixed (catheterization and spontaneous void), Spontaneous void only, Mixed (Intermittent balloon catheter and spontaneous void), CIC and Intermittent balloon catheter or Mixed (CIC, Intermittent balloon catheter and spontaneous void))
 - Urodynamics
 - ✧ Maximum cystometric capacity (MCC)
 - ✧ Maximum detrusor pressure during the first involuntary detrusor contraction (IDC) ($P_{\max IDC}$)
 - ✧ Volume at first involuntary detrusor contraction ($V_{P_{\max IDC}}$)
 - ✧ Maximum detrusor pressure during the storage phase ($P_{\det Max}$)
- Age ranges (for EudraCT requirement)

